Although classical radiation biology states that the cytotoxic effects of radiation on tumor cells are primarily initiated by DNA double strand breaks, there is an emerging understanding of the importance of an “immunogenic cell death” (ICD) as a significant *in vivo* cell death mode. Radiation has been shown to induce all 3 key components of ICD: cell surface translocation of calreticulin to signal dendritic cells, and release of danger signals such as HMGB1 and ATP, which result in priming of CD8+ T-cells²¹. Tumor mutational burden and defects in the DNA repair pathway have been linked to tumor response rate to checkpoint inhibitors such as anti-PD-1 therapy. While bladder cancer is the third highest mutated cancer²², high RBE particle therapy such as neutrons cause qualitative changes in the sub-cellular distribution and types of DNA damage, and have the potential to shift cells from an apoptotic cell death mode towards the more inflammatory, and possibly immunogenic, mitotic catastrophe and necrotic cell death modes.²³⁻²⁵ High RBE therapy may cause a more immunogenic tumor microenvironment via release of more tumor neoantigens^{26,27}. Mouse total body radiation experiments in the 1970s with neutrons versus standard photons found that the degree of immunosuppression was dependent on the LET of the radiation (neutrons have high LET), and mortality from total body radiation differs based on LET, for the same delivered radiation dose²⁸.

Immunologic changes in peripheral blood of patients receiving immunotherapy:

Immune profiling of peripheral blood from patients on checkpoint inhibitor immunotherapy has not been widely explored. Huang *et al.* looked at peripheral blood of 29 patients with metastatic melanoma receiving anti-PD-1 antibody pembrolizumab²⁹. At 3-weeks into therapy, frequency of Ki67+ CD8 T-cells peaked and then declined, with highest percent of Ki67+ CD8 T-cells around weeks 3-6 after start of pembrolizumab (Ki67+ CD8 T-cells increased from around 7% at baseline to around 14-19% at weeks 3-6 post-pembrolizumab). The increase in Ki67 expression was mostly seen in the PD-1+ versus PD-1 negative CD8 T-cells, with Ki67 increasing from around 9% at baseline to around 23% at 3-weeks (peak response) in the PD-1+ CD8 T-cells population, and non-statistically significant increase in Ki67+ cells in the PD-1 negative CD8 T-cell population (Figure 1). Clinical response was correlated with the fold change of PD-1+ Ki67+ CD8 T-cells after

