Complete response, partial response, or stable disease	Cannot have met criteria for progression before complete response, partial response, or stable disease	Can have had iUPD (one or more instances), but not iCPD, before iCR, iPR, or iSD
Confirmation of complete response or partial response	Only required for non-randomised trials	As per RECIST 1.1
Confirmation of stable disease	Not required	As per RECIST 1.1
New lesions	Result in progression; recorded but not measured	Results in iUPD but iCPD is only assigned on the basis of this category if at next assessment additional new lesions appear or an increase in size of new lesions is seen (≥ 5 mm for sum of new lesion target or any increase in new lesion non-target); the appearance of new lesions when none have previously been recorded, can also confirm iCPD
Independent blinded review and central collection of scans	Recommended in some circumstances—eg, in some trials with progression-based endpoints planned for marketing approval	Collection of scans (but not independent review) recommended for all trials
Confirmation of progression	Not required (unless equivocal)	Required
Consideration of clinical status	Not included in assessment	Clinical stability is considered when deciding whether treatment is continued after iUPD

“i” indicates immune responses assigned using iRECIST. RECIST=Response Evaluation Criteria in Solid Tumours. iUPD=unconfirmed progression. iCPD=confirmed progression. iCR=complete response. iPR=partial response. iSD=stable disease.

Table 1: Comparison of RECIST 1.1 and iRECIST

B	Timepoint response with no previous iUPD in any category	Timepoint response with previous iUPD in any category*
Target lesions: iCR; non-target lesions: iCR; new lesions: no	iCR	iCR
Target lesions: iCR; non-target lesions: non-iCR/non-iUPD; new lesions: no	iPR	iPR
Target lesions: iPR; non-target lesions: non-iCR/non-iUPD; new lesions: no	iPR	iPR
Target lesions: iSD; non-target lesions: non-iCR/non-iUPD; new lesions: no	iSD	iSD
Target lesions: iUPD with no change, or with a decrease from last timepoint; non-target lesions: iUPD with no change, or decrease from last timepoint; new lesions: yes	Not applicable	New lesions confirm iCPD if new lesions were previously identified and they have increased in size (≥5 mm in sum of measures for new lesion target or any increase for new lesion non-target) or number; if no change is seen in new lesions (size or number) from last timepoint, assignment remains iUPD

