3.1 General Design

This is a study to test whether densely ionizing, high relative biologic equivalence (RBE) radiation in the form of neutron radiation, can improve the response rate to checkpoint inhibitor immunotherapy in patients with advanced urothelial carcinoma. In this trial, the addition of focal radiation is hypothesized to act as a “vaccine” by releasing tumor neoantigens, with the goal being to augment the immune response. Trial schema is shown below in Figure 1 and study calendar in Table 1. Patients with advanced urothelial carcinoma about to receive checkpoint inhibitor therapy (pembrolizumab), with at least two sites of measurable disease per RECIST 1.1, will undergo neutron radiation to 1-3 sites of disease. At least one site of RECIST 1.1 evaluable disease must remain untreated³¹, as only non-radiated sites will serve as index lesions to assess for response rate per iRECIST criteria.³⁰ Asymptomatic lesions are eligible for radiation as the primary goal of the radiation therapy is to induce an immune response.

[figure not shown]

Figure 2. Clinical trial schema.

Table 1. Study Calendar.

	Pre-treatment⁴	Between Dose 2 and 3 of Immunotherapy⁵	4-Weeks After End of Radiation⁶	16-Weeks After End of Radiation⁷
Informed Consent	X			
Medical History	X		X	X
Physical Exam	X		X	X
ECOG Performance Status	X		X	X
Blood Draw¹	X	X	X	X
Radiation Therapy		X		
Tumor biopsy (optional)²		X		X
CT C/A/P³	X		X	X

¹Blood draw will consist of 9 tubes: 8 yellow top tubes (BD Vacutainer #364606 Acid citrate dextrose additives ACD Solution A) and 1 red top tube (BD Vacutainer #367820 Clot Activator) to collect and store the following: 1) 6 tubes of 0.5 ml serum; 2) 2 tubes of 1.0 ml plasma; 3) 4 tubes of 0.5 ml PBMC; and 4) 6 tubes of 1 ml PMBC.

²Tumor biopsy of a radiated or non-radiated site will be performed for patients who consent.

³CT C/A/P is preferred but MRI or PET/CT also acceptable.

⁴All pre-treatment assessments must be performed within 30 days of protocol enrollment, except CT C/A/P which must be within 45 days of protocol enrollment.

Pembrolizumab is typically given every 3 weeks. Dose 2 must happen between 2.5-5 weeks after dose 1, and dose 3 must happen between 6-9 weeks after dose 1.

⁶Acceptable date range is 3 to 6 weeks after radiation ends.

⁷Acceptable date range is 12 to 24 weeks after radiation ends.

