Time points for peripheral blood collection are based on prior studies, including Huang *et al.* and Twyman-Saint Victor *et al.* described above^{9,29}, that show peak changes in peripheral blood immune cell populations around 3-6 weeks post start of therapy for checkpoint inhibitor immunotherapy, and changes after radiation treatment that peak around 2-4 weeks but can persist for months after treatment.

After the study period as outlined above, all patients will be followed at least once every 3 months by the treating oncologist per standard of care. Toxicity, disease response, and survival will be recorded at each clinic visit. Patients are considered off-study once disease progression is detected per iRECIST³⁰. Follow up with radiation oncology is not required but records will be obtained from treating oncologist. All correlative studies will be batched for analysis.

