3.2. Statistical Plan

This is a single-arm phase 2 study with the primary endpoint of overall response rate per iRECIST. Overall response rate will be calculated as the percentage of patients achieving a PR or CR, and will be presented along with the 95% CI. Historical data suggest a response rate of 20%, and we hypothesize a true response rate of 40% with the proposed treatment. With 20 patients, we'll have 80% power to observe an estimated response rate that is statistically significantly higher (at the one-sided significance level of .05) than the fixed rate of 20%. Secondary endpoints overall and progression-free survival will be estimated using the method of Kaplan and Meier with 95% CI obtained using Greenwood estimates of variance. Toxicities as assessed by CTCAE version 4.0 will be summarized as the proportion of patients with such toxicities, in addition to total number of toxicities (allowing for multiple toxicities within a patient) among all patients. The exploratory endpoints, change in peripheral blood cell populations will be assessed by estimating the average change between pre- and post-treatment, and these differences will be calculated for each time point; the one-sample t-test will be used to test the null hypothesis that the change is equal to zero. Trends for changes in differences from pre-treatment to post-treatment across time will be assessed using generalized linear models. Similar methods will be used to assess change in tumor biopsies for patients who consent to such analyses, where changes from pre- to post-treatment will be examined for cell death, tumor-infiltrating lymphocytes and expression of various cell-surface markers.

Should this regimen be deemed to be potentially efficacious as defined above, consideration will be given to conduct a subsequent randomized study designed to compare neutron radiation plus checkpoint inhibitors versus checkpoint inhibitors alone.

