6.1 Duration of Therapy

Pembrolizumab therapy will continue until one or more of the following conditions are met:

- The subject withdraws consent.
- Confirmed radiographic disease progression
- Unacceptable adverse experiences
- Intercurrent illness that prevents further administration of treatment
- Investigator's decision to withdraw the subject
- The subject has a confirmed positive serum pregnancy test
- Noncompliance with trial treatment or procedure requirements
- The subject is lost to follow-up
- Administrative reasons

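### The 16-week mean blood-marker change may rest on fewer, probably better-faring patients than the 4-week mean, and section 3.2 has no step that separates this selection from immune change

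*Combined protocol and SAP*

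**What the plan says.** The study calendar (Table 1 in section 3.1) has blood draws before treatment, between pembrolizumab doses 2 and 3, and at 4 and 16 weeks after radiation (windows 3 to 6 and 12 to 24 weeks). The only post-baseline CTs in the calendar fall at the 4- and 16-week visits.

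On leaving the study, section 3.1 says: "Patients are considered off-study once disease progression is detected per iRECIST". It does not say whether this means unconfirmed progression (iUPD) or confirmed progression (iCPD). The sentence stands in a paragraph that opens "After the study period as outlined above, all patients will be followed at least once every 3 months", so it may concern later follow-up only. Nothing says whether calendar draws continue once a patient is off-study.

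For the blood endpoints, section 3.2 averages the change from pre-treatment at each time point, and "the one-sample t-test will be used to test the null hypothesis that the change is equal to zero". The trend is covered by "Trends for changes in differences from pre-treatment to post-treatment across time will be assessed using generalized linear models". No analysis set, within-patient correlation or missing-data method is given.

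The Introduction gives a reason to expect marker and outcome to be linked. It reports, from a melanoma study of pembrolizumab, "Clinical response was correlated with the fold change of PD-1+ Ki67+ CD8 T-cells after" anti-PD-1 therapy, adjusted for baseline tumor burden.

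**The concern.** The 4-week mean includes patients who later die or leave. The 16-week mean may not. If those lost had a smaller immune change than those who stayed, the mean rises from 4 to 16 weeks although no patient's value has moved. A model that treats the draws as independent passes that rise straight into the trend.

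Persistence is a question that the protocol itself raises: section 3.1 notes that changes after radiation may last for months. A selection effect could therefore be reported as a lasting immune effect of neutrons plus pembrolizumab.

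**Working it through.** **The plan's own figure.** There is none for the blood endpoints. The only design calculation concerns the response rate, and this point does not depend on it.

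**Who can be missing at 16 weeks**

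| Patient | Off-study at iUPD | Off-study at iCPD |
|---|---|---|
| Dies before the draw | missing | missing |
| Progression on the 4-week CT | missing, if draws stop at off-study | can be drawn, unless confirmed earlier on an unscheduled scan |
| Progression confirmed between visits on unscheduled imaging | missing, if draws stop | missing, if draws stop |
| First progression on the 16-week CT | can be drawn at that visit | can be drawn at that visit |

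The second row follows from the calendar. The 4-week CT is the first post-baseline calendar scan, and iRECIST as reproduced in section 2 requires confirmation, so on the calendar alone that scan can show only iUPD. The next calendar scan is at the 16-week visit.

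**How large the loss could be.** The documents give no progression rate. For deaths, the Introduction gives a median survival of 10.3 months on pembrolizumab after platinum. Exponential survival is my assumption.

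- On dose timing, the calendar says "Dose 2 must happen between 2.5-5 weeks after dose 1, and dose 3 must happen between 6-9 weeks after dose 1". With radiation between those doses, the last draw falls between 2.5 + 12 = 14.5 and 9 + 24 = 33 weeks after dose 1.
- At 4.345 weeks per month, that is 3.34 to 7.59 months. Deaths by then: 1 − 0.5^(3.34/10.3) = 20% to 1 − 0.5^(7.59/10.3) = 40%, or 4 to 8 of 20.
- Some of these deaths would precede the 4-week draw and affect both means. Over the nominal 12 weeks between the two draws (2.76 months), the figure is 1 − 0.5^(2.76/10.3) = 17%. A total loss of 30-50% between the draws therefore needs progression to supply the rest.

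**Size of the shift, constant-gap model.** Let f be the share lost between the draws, and d the difference in mean change (in SD) between those who stay and those lost, equal at both visits. The 4-week mean is (1 − f)·m_stay + f·m_lost and the 16-week mean is m_stay. The difference is f × d with no true change.

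| f | d = 0.5 | d = 1.0 |
|---|---|---|
| 0.3 | 0.15 | 0.30 |
| 0.5 | 0.25 | 0.50 |

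**Second model, as a check.** Suppose patients are lost according to a latent progression score with correlation ρ to the 16-week change. The mean of those left shifts by ρ·φ(c)/(1 − f), where c is the f-quantile of the standard normal.

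- f = 0.3: φ(c) = 0.348, so 0.348/0.7 = 0.497. The shift is 0.15 SD (ρ = 0.3) or 0.25 SD (ρ = 0.5).
- f = 0.5: 0.399/0.5 = 0.798. The shift is 0.24 or 0.40 SD.
- ρ = 0: no shift.

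In simulation with 20 patients and a true mean change of zero, a two-sided 5% t-test at 16 weeks then rejects about 8-15% of the time at 30% loss and 12-23% at 50% loss.

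**What a different analysis does.** I simulated three post-baseline changes per patient with within-patient correlation 0.6.

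- Constant-gap model: a random-intercept mixed model leaves about 0.03-0.10 SD. The 4-to-16-week contrast in patients with both draws leaves about 0.
- Loss driven by the 16-week value itself: the same-patient contrast keeps (1 − 0.6) = 40% of the shift, for example 0.4 × 0.25 = 0.10 SD. Across the two analyses the reduction is about 40-70%. If loss were unrelated to the 4-week value, the same-patient contrast would give no reduction.

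**The case against.** A reader might infer that the 16-week draw exists only for patients without progression. The documents do not support that. The iRECIST comparison in section 2 says that a patient "Can have had iUPD (one or more instances), but not iCPD, before iCR, iPR, or iSD", so unconfirmed progression does not end response assessment. Section 6.1 likewise lists "Confirmed radiographic disease progression" as the imaging ground for ending pembrolizumab. The table above shows which progressors can still be drawn.

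A reader might also infer that a rise at 16 weeks is certain. It is not. The shift is zero without a link between marker and progression, and for suppressive cells such as MDSC it could run the other way. The cited evidence is one marker in 29 melanoma patients. Response was 8/20 above and 2/7 below a cutoff that the protocol calls arbitrary: odds ratio (8 × 5)/(12 × 2) = 1.67, or ln(1.67) × √3/π = 0.28 SD. With response standing in for progression, 30-50% loss would give only 0.08-0.14 SD. The standard error of a mean of 14 to 10 patients is 1/√14 = 0.27 to 1/√10 = 0.32 SD. This stands, and it places the 0.15-0.50 SD range towards the upper side of what that one source suggests.

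Section 3.2 already analyses change from pre-treatment, which is a within-patient quantity. That is true, but averaging the changes over different patients at each visit brings the problem back. Finally, the peaks that section 3.1 expects fall at the earlier draws, before most of the loss, which limits the harm.

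**Conclusion.** The point holds as a minor one. Death depletes the 16-week draw on any reading, and progression may do so, depending on an off-study term that section 3.1 leaves undefined. The protocol's own background gives some reason to think this loss is related to the marker. The planned per-visit means and trend model cannot distinguish persistence from selection.

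The size is about 0.15-0.50 SD for 30-50% loss and a 0.5-1.0 SD gap, and nil if marker and progression are unrelated. Loss, gap and correlation are all assumptions, because the documents give none of them. The consequence is confined to exploratory endpoints. The response-rate test, and the decision on a randomized follow-on study that rests on it, are untouched.

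**What to change.** **Section 3.2.**
- Replace the generalized linear model for trend with a linear mixed model that has a patient random intercept and uses all available draws.
- Show the 4- and 16-week mean changes in the same patients, namely those with both draws.
- Report the number sampled at each visit by progression status, with deaths shown separately.

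**Section 3.1.**
- State that the scheduled 16-week research draw is still taken after progression where the patient is willing and attending. An extra draw on leaving would not serve instead: for a patient who leaves at the 4-week visit, it is the 4-week draw.
- Reconcile the off-study wording with the iRECIST confirmation rules and with section 6.1, so that it is clear which event takes a patient off-study and whether calendar draws then stop.

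**Cost.** A few sentences, a little more analysis and a few blood draws. Some progressing patients will decline or will have started other therapy, which should be recorded with the sample. The analyses reduce the bias but do not remove it if dropout depends on the unobserved 16-week value, and no draw can be recovered for patients who have died. The sampling sentence needs to be in place early, because a draw that was not taken cannot be replaced.

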3.3. Eligibility Criteria

A. Inclusion Criteria

- Pathologically proven (either histologic or cytologic) diagnosis of urothelial carcinoma
- At least two sites of disease that are measurable by RECIST 1.1 criteria
- Eligible for checkpoint inhibitor immunotherapy (pembrolizumab) per standard of care
- No history of autoimmune disease requiring systemic therapy (e.g. steroids or biologic agents).
- Adequate organ function
 - Hematologic
 - ANC ≥ 1500 /mCL
 - Platelets $\geq 100,000$ /mCL
 - Hemoglobin > 9 g/dL
 - Renal
 - Creatinine ≤ 1.5 x upper limit of normal (ULN) OR ≥ 60 mL/min
 - Hepatic
 - Total bilirubin ≤ 1.5 ULN OR direct bilirubin \leq ULN if total bilirubin > 1.5 x ULN
 - AST and ALT ≤ 2.5 x ULN OR < 5 x ULN if patient has live metastasis
 - Albumin ≥ 2.5 g/dL
 - Coagulation
 - INR or PT ≤ 1.5 x ULN unless on anticoagulation therapy, in which case PT or PTT should be in the therapeutic range
 - PTT ≤ 1.5 x ULN unless on anticoagulation therapy, in which case PT or PTT should be in the therapeutic range

- Eligible for neutron radiation treatment to 1-3 sites of metastatic disease (lesions do not have to be symptomatic)
- No steroids for at least 2 weeks prior to enrollment, and patient must not be expected to require steroids during the study period
- Zubrod Performance Status 0-2
- Age \geq 18
- Patient must sign study specific informed consent prior to study entry
- Patients who are sexually active must use medically acceptable forms of contraception
- Life expectancy must be $>$ 3 months

B. Exclusion Criteria

- Has a known history of active TB (Bacillus Tuberculosis)
- Hypersensitivity to pembrolizumab or any of its excipients
- Has a known additional malignancy that is progressing or requires active treatment
- Has received prior therapy with an anti-PD-1, anti-PD-L1, or anti-PD-L2 agent.
- Has a known history of Human Immunodeficiency Virus (HIV) (HIV 1/2 antibodies).
- Has known active Hepatitis B (e.g., HBsAg reactive) or Hepatitis C (e.g., HCV RNA [qualitative] is detected).
- Has known psychiatric or substance abuse disorders that would interfere with cooperation with the requirements of the trial
- Has a history or current evidence of any condition, therapy, or laboratory abnormality that might confound the results of the trial, interfere with the subject's participation for the full duration of the trial, or is not in the best interest of the subject to participate, in the opinion of the treating investigator.
- Has known history of, or any evidence of active, non-infectious pneumonitis.
- Has an active infection requiring systemic therapy.
- Has received a live vaccine within 30 days of planned start of study therapy.
- Has known active central nervous system (CNS) metastases and/or carcinomatous meningitis. Subjects with previously treated brain metastases may participate provided there is no evidence of new or enlarging brain metastases, and are not using steroids for at least 7 days prior to trial treatment. This exception does not include carcinomatous meningitis which is excluded regardless of clinical stability.

4 Study Registration

Subjects will be registered by the FHCRC/UW Study Coordinator and entered into the Protocol Accrual Tracking System (PATS). Information regarding the PATS system is available at http://www.cancerconsortiumorg/rto/protocol_office/pats/. A complete, signed, study consent and HIPAA consent are required for registration.

5 Radiation Therapy

All radiation treatments will be administered at the University of Washington Medical Center. All other appointments (medical oncology visits, labs, scans, etc.) can occur at either UWMC or SCCA. Protocol treatment must begin within 30 days of study enrollment.

